8.3.3. Reporting of Adverse Events and Serious Adverse Events

The AE reporting period begins from the time that the subject signs the ICF through and including 30 calendar days after the last study intervention dose. All subjects with treatment-related AEs/SAEs should be observed until resolution or stabilization. Any SAE occurring after the reporting period must be promptly reported if a causal relationship to the investigational drug is suspected. If the subject begins a new anticancer therapy, the safety reporting period ends at the time the new treatment is started, however, death must always be reported if it occurs during the AE reporting period irrespective of intervening treatment.

Elective or previously scheduled hospitalizations for pre-existing conditions that have not worsened after initiation of treatment should not be classified as SAEs. For example, an admission for a previously scheduled ventral hernia repair would not be classified as an SAE.

All AEs should be recorded individually unless, in the opinion of the Investigator or designated physician, the AEs constitute components of a recognized condition, disease, or syndrome. In the latter case, the condition, disease, or syndrome should be reported rather than each individual sign or symptom. If a constellation of signs and/or symptoms cannot be medically characterized as a single diagnosis or syndrome at the time of reporting, each individual event should be recorded as an AE or SAE as appropriate on the relevant form(s) (SAE Report Form and/or AE CRF). If a diagnosis is subsequently established, it should be reported as follow-up information becomes available. If a diagnosis is determined after the reporting of the constellation of symptoms, the signs/symptoms should be updated to reflect the diagnosis.

Each AE will be evaluated for duration, severity, seriousness, and causal relationship to the investigational drug. The action taken with study intervention and the outcome must also be recorded.

All SAEs, regardless of relationship to the study intervention, must be reported immediately (within 24 hours of awareness of event by Investigator) to the Sponsor and Contract Research Organization (CRO) pharmacovigilance group. Initial SAE notification should be made by e-mailing or faxing the SAE report form to the e-mail or fax number provided on the SAE report form.

An initial SAE Report may be sent without the Investigator's signature but must be followed by a report signed by the Investigator within 48 hours of becoming aware of the event. Follow-up SAE reports must be submitted by the Investigator as new information becomes available.

The Medical Monitors for this study may be contacted for advice or assistance. Contact details will be provided in the study contact list.

8.3.4. Severity of Adverse Events

The severity of the AE will be graded according to the National Cancer Institute (NCI) CTCAE, version 5.0 (see web page https://ctep.cancer.gov/protocolDevelopment/electronic_applications/ctc.htm#ctc_50 for details). AEs not listed in the CTCAE should be graded as summarized in Table 9.

Table 9: CTCAE AE Grading

CTC Grade	Equivalent To:	Definition
Grade 1	Mild	Discomfort noticed but no disruption of normal daily activity
Grade 2	Moderate	Discomfort sufficient to reduce or affect daily activity; no treatment or medical intervention is indicated although this could improve the overall well-being or symptoms of the subject
Grade 3	Severe	Inability to work or perform normal daily activity; treatment or medical intervention is indicated to improve the overall well-being or symptoms; delaying the onset of treatment is not putting the survival of the subject at direct risk
Grade 4	Life-threatening/disabling	An immediate threat to life or leading to a permanent mental or physical condition that prevents work or performing normal daily activities; treatment or medical intervention is required to maintain survival
Grade 5	Death	AE resulting in death

Abbreviations: AE: adverse event, CTC: Common Terminology Criteria; CTCAE: Common Terminology Criteria for Adverse Events.

8.3.5. Relationship of Adverse Events to Study Intervention

The Investigator will make a judgment regarding whether or not the AE was related to study intervention, as outlined below:

- **Definitely related:** This category applies when, after careful medical consideration, there is almost no consideration of other causation.
- **Probably related:** There is a clinically plausible time sequence between onset of the AE and study intervention administration. The AE is unlikely to be caused by a concurrent or underlying illness, other drugs, or procedures. If applicable, the AE follows a clinically consistent resolution pattern upon withdrawal of study intervention.
- **Possibly related:** There is a clinically plausible time sequence between onset of the AE and study intervention administration, but the AE could also have been caused by the concurrent or underlying illness, other drugs, or procedures. Information regarding study intervention withdrawal may be lacking or unclear. "Possible" should be used when study intervention administration is one of several biologically plausible causes of the AE.

- **Unlikely related:** The AE is most likely due to a cause not related to study intervention administration. However, association with the study intervention cannot be completely ruled out.
- **Unrelated:** Another cause of the AE is most plausible, and a clinically plausible temporal sequence is inconsistent with the onset of the AE and study intervention administration and/or a causal relationship is considered biologically implausible.

For the purpose of regulatory reporting requirements, causal relationships of definite, probable, and possible will be considered treatment-related, while unlikely and unrelated will be considered not treatment-related.

8.3.6. Clinical Laboratory Adverse Events

A clinical laboratory AE is any laboratory value that is deemed clinically significant by the Investigator. The Investigator should decide, based upon the AE criteria and the clinical condition of the subject, whether a change in a laboratory parameter is clinically significant and therefore represents an AE.

The following items may be considered when determining clinical significance:

- Severity of the laboratory abnormality (i.e., greater than Grade 2 in severity)
- Laboratory abnormality requires a medical intervention
- Laboratory abnormality requires a change or suspension of study intervention
- Laboratory abnormality is accompanied by clinical symptoms

Laboratory abnormalities that are not considered clinically significant should not be recorded as AEs and will be captured and reported in the laboratory section of the clinical study report. If a medical intervention occurs, it should be recorded as a treatment with the abnormal laboratory finding as the AE (e.g., anemia with treatment required and blood transfusion recorded as a procedure, hyperglycemia with treatment required and change in insulin dose recorded on concomitant medications).

If, at the end of the treatment phase with the study intervention, there are pathological laboratory values which were not present at Baseline, further clinical or laboratory investigations should be performed until the values return to within reference range or until a plausible explanation (i.e., concomitant disease) is found for the pathological laboratory values.

8.3.7. Regulatory Aspects of Adverse Event Reporting

The Sponsor is responsible for submitting reports of SAEs associated with the use of the study intervention to the appropriate Regulatory Authority (e.g., the US FDA), Investigators, and IRB/IEC/Central Ethics Committee (CEC) in accordance with all applicable regulations and guidelines.

It is the responsibility of the Investigator to notify the IRB of all SAEs that occur at his or her site. Investigators will be notified of all suspected, unexpected serious adverse reactions (SUSARs; 7 / 15 Day Safety Reports) that occur during any clinical studies that are using the investigative compound. Each site is responsible for notifying their IRB/IEC/CEC of these additional SUSARs in accordance with local regulations.

8.3.8. Overdose

In the case of overdose, clinic staff should be notified immediately, and supportive care should be given if needed and as indicated. Subjects should be informed to contact their doctor immediately if they have taken an overdose and should stop taking duvelisib.

For this study, overdose is defined as a daily dose of duvelisib higher than the prescribed daily dose. Overdoses will not be considered SAEs unless the outcome of the overdose meets seriousness criteria as defined in Section 8.3.2. In the event of an overdose that causes an SAE, the Sponsor should be notified within 24 hours of Investigator's knowledge. The subject should be carefully monitored for potential adverse reactions and symptomatic treatment instituted as per institutional standards of care. The Investigator will determine if and when dosing should resume.

8.3.9. Pregnancy

Any pregnancy must be reported to the Sponsor or designee within 24 hours of the Investigator's knowledge of the pregnancy using a Pregnancy Report Form.

Pregnancy per se is not considered an AE unless there is cause to believe that the study intervention may have interfered with the effectiveness of a contraceptive medication or if the outcome of the pregnancy meets SAE criteria (miscarriage or congenital anomaly/birth defect, etc.), in which case it should be reported in the same manner and timelines as an SAE. In addition, any infant death or congenital anomaly occurring after 30 days that the Investigator suspects is related to the in-utero exposure to the study intervention should also be reported as an SAE. Hospitalization for normal delivery of a healthy newborn is not an SAE.

Since duvelisib has not been evaluated in pregnant or nursing women, the treatment of pregnant women or WCBP who are not using highly effective contraception is contraindicated (see Table 18 and Section 10.4 for instructions on pregnancy testing and contraception).

Pregnancies occurring in subjects or partners of male subjects during the study intervention period until 30 days after the subject's last dose of study intervention are considered immediately reportable events. If a pregnancy occurs in a subject, study intervention must be discontinued immediately. The pregnant woman should be referred to an obstetrician/gynecologist experienced in reproductive toxicity for further evaluation and counseling. The Investigator will observe the pregnant woman until completion of the pregnancy and must notify the Sponsor of the outcome within 24 hours of the Investigator's knowledge of the pregnancy outcome using a Pregnancy Outcome Form. This notification includes pregnancies resulting in live, "normal" births.

8.4. Quality of Life Assessments

8.4.1. ECOG Performance Status

ECOG Performance Status will be assessed at Screening. If the ECOG Performance Status assessed at Screening is performed within 7 days of Cycle 1 Day 1, the Screening assessment can be used and does not need to be repeated at Cycle 1 Day 1 (predose). Please see SoA Table 1 for the schedule of ECOG Performance Status during study treatment and follow-up.

8.4.2. Subject Self-reported Health-related Quality of Life

Subject self-reported health-related quality of life (QoL) will be assessed at Screening, during study treatment, and, when possible, upon treatment discontinuation for any reason. Subject-reported health-related QoL will be assessed using the EQ-5D-3L questionnaire. Questionnaire should be administered predose and prior to other procedures during treatment visits.

8.5. Pharmacokinetics

- Blood samples will be collected to evaluate the PK of duvelisib and metabolite IPI-656 at the visits and timepoints defined in SoA [Table 2](#).
- Predose samples are preferred, therefore on the days that include PK assessments the morning dose of duvelisib should be administered in the clinic to facilitate collection of samples prior to dosing. However, the sample should still be collected even if the morning dose of duvelisib has already been taken. The date and time of the sample collection and date and time of the previous duvelisib dose must be recorded for all collected samples.
- Additional PK samples beyond those listed in SoA ([Table 2](#)) may be requested (when feasible) for any unusual safety event. (i.e., an AE different in type and severity from that which is expected in the setting of duvelisib use).
- Specific instructions on sample collection and handling will be provided in a separate Laboratory Manual.
- Retained duplicate PK samples may also be used to evaluate safety or efficacy aspects related to concerns arising during or after the study.
- Genetic analyses will not be performed on these PK samples.
- Subject confidentiality will be maintained.

8.6. Pharmacodynamics

Pharmacodynamic biomarkers will be assessed using blood samples collected at sampling timepoints in the SoA ([Table 2](#)) and are described under Biomarkers (Section 8.8).

8.7. Genetics

Normal germline genetic studies are not evaluated in this study. Tumor genomic studies may be conducted as part of exploratory biomarker research (Section 8.8).

8.8. Biomarkers

Biomarker samples will be collected according to the SoA ([Table 2](#)) and assessments may be conducted to evaluate potential biomarkers as described in [Table 10](#).

Table 10: Biomarker Samples and Assessments

Sample	Assessments
Blood for pharmacodynamics	Pharmacodynamic assays evaluate phosphorylated protein levels in several cell types.
Serum and plasma for biomarker analysis	Protein (e.g., cytokines, chemokines) and/or ctDNA
Blood for immunophenotyping	Immune cell population profiling (e.g., B T- funcDNA, and/or RNA analysis)
Stool for biomarker analysis	Protein, DNA, and/or RNA analysis to evaluate correlations with gastrointestinal toxicities
Archival tumor tissue (if available)	Tumor markers that may predict clinical response to duvelisib. PI3K pathway and/or disease-specific biomarkers (e.g. PTEN, PI3K isoforms) by immunohistochemistry and/or in situ hybridization. Tumor genomic studies may be performed (e.g. DNA sequencing, DNA copy number analysis, RNA expression profiling) to explore whether specific genomic features correlate with response or resistance to duvelisib in iNHL.
Colon biopsies taken as standard of care to assess colitis (if available)	Pharmacodynamic analysis, immune cell and immune cell function, protein and genomics analyses

Abbreviations: ctDNA: circulating tumor deoxyribonucleic acid; iNHL: indolent non-Hodgkin lymphoma; PI3K: phosphoinositide 3-kinase; PTEN: phosphatase and tensin homolog; RNA: ribonucleic acid

In addition, C-reactive protein levels in blood (a clinical safety laboratory assessment) will be evaluated as a potential biomarker and will be assessed at Screening and whenever Grade ≥ 2 diarrhea or any colitis occurs.

8.9. Medical Resource Utilization and Health Economics

Health Economics/Medical Resource Utilization and Health Economics parameters are not evaluated in this study.

9. STATISTICAL METHODOLOGY

A detailed description of the statistical methodology for this study can be found in the Statistical Analysis Plan (SAP). Deviations from the statistical analyses outlined in this protocol will be indicated in the SAP; any further modifications will be noted in the final clinical study report.

9.1. Statistical Hypotheses

This study will test the null hypothesis that the ORR for each arm is $\leq 30\%$ against the alternative that ORR is $\geq 55\%$.

9.2. Sample Size Determination

The sample size for each arm was calculated using a 2-stage approach.

For each arm: in the first stage, 15 subjects will be randomized. The evaluation of the first stage will take place after the 15 enrolled subjects have been followed for a minimum of 3 cycles (18 weeks).

If there are fewer than 6 responders (PR or CR) among the first 15 subjects, consideration may be given to terminating the treatment arm. The decision to proceed to Stage 2 will be based on the totality of data observed, including types of responses, safety data, and discontinuation rates. The treatment arm may also not proceed to the second stage if the totality of the data is viewed as compelling; such scenarios could include (but are not limited to) accumulating enough data in Stage 1 to conclude the ORR exceeds 30%. If the treatment arm proceeds to the second stage, up to 36 additional subjects will be enrolled for a total of 51. If fewer than 22 (43%) responders (PR or CR) are observed in 51 subjects, consideration may be given to concluding that the treatment schedule does not warrant further study in this population. The final evaluation of each schedule will be based on the totality of data observed, including types of responses, safety data, and discontinuation rates. This design yields 90% power under the assumptions described above; the alpha level (type I error rate) for the study will be controlled at 0.025.

Subjects will be stratified by number of prior therapies (1 or > 1), bulky disease status (longest diameter of baseline lesion < 5 cm or ≥ 5 cm) and time since last recurrence (≥ 24 months or < 24 months).

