**Figure 1: Treatment Scheme**

Solid sections: duvelisib 25 mg BID; hashed sections: drug holiday. Subjects will be randomized 1:1 to Arms 1 and 2. Subjects will be assessed for disease response on Day 1 of Cycles 2, 4, 6, 9, 13, 17 and every fourth cycle thereafter until disease progression, unacceptable toxicity or withdrawal.

Abbreviations: BID: twice daily.

The study has a 2-stage design. For each arm: in the first stage, 15 subjects will be enrolled. Responses will be assessed by the Investigator according to the 2007 revised IWG criteria (Cheson 2007) (primary endpoint) and the 2014 Lugano criteria (Cheson 2014). The evaluation of the first stage will take place after the enrolled subjects have been followed for a minimum of 3 cycles. If there are fewer than 6 responders (partial response (PR) or complete response (CR)) among the first 15 subjects per arm, consideration may be given to stopping that arm. A treatment arm may also not proceed to the second stage if the totality of the data is compelling (e.g., accumulating enough data in Stage 1 to conclude the overall response rate (ORR) exceeds 30%). Otherwise, approximately 36 additional subjects will be enrolled for a total of 51 per arm. Enrollment will be continuous between Stage 1 and Stage 2. If fewer than 22 (43%) responders (PR or CR) are observed in 51 subjects, consideration may be given to concluding that the treatment schedule does not warrant further study in this population. Each arm will be evaluated separately.

It is anticipated that study enrollment will occur over approximately 2 years. The last subject visit will occur 2 years after the last subject is randomized. If the study ends prior to all subjects discontinuing treatment, any subject continuing to receive benefit will be provided the opportunity to continue to receive duvelisib. Long-term continued treatment may be provided via an expanded access program consistent with local regulations, such as the Secura Bio NPP. Study procedures and their timing are summarized in the schedule of assessments (SoA) (Protocol Section 1.3).

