#### 4.10.1.5 Interim Analyses

No formal interim analysis is planned. Study data for each arm will be evaluated at the end of Stage 1 to determine whether a study arm should be terminated or continued to Stage 2. Please see additional details of the 2-stage design in [Section 4.13](#) below.

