#### 4.10.2 Primary Efficacy Variable – ORR

The ORR (proportion of subjects achieving a CR or PR using the number of subjects in the mITT analysis set as the denominator) will be estimated, along with the 2-sided 95% exact CI using the Clopper-Pearson exact method for binomial proportions. Responses for the primary ORR analysis will be assessed using the 2007 revised IWG criteria (Cheson 2007). Missing data will be imputed by assuming that any subjects not exhibiting a response (CR or PR) are non-responders. Responses occurring after the start of subsequent anticancer therapy will not be included in the numerator.

The primary analysis of ORR will be performed 12 months after the last subject is randomized, using the time windows specified in [Section 4.2](#) as applicable.

A by-subject listing of the primary efficacy data will be provided.

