### 4.13 Determination of Sample Size

The sample size for each arm was calculated using a 2-stage approach.

For each arm: in Stage 1, 15 subjects will be randomized. The evaluation of the first stage will take place after the 15 enrolled subjects have been followed for a minimum of 3 cycles (18 weeks).

If there are fewer than 6 responders (PR or CR) among the first 15 subjects, consideration may be given to terminate the treatment arm. The decision to proceed to Stage 2 will be based on the totality of data observed, including types of responses, safety data, and discontinuation rates. The treatment arm may also not proceed to Stage 2 if the totality of the data is viewed as compelling;

such scenarios could include (but are not limited to) accumulating enough data in Stage 1 to conclude the ORR exceeds 30%. If the treatment arm proceeds to Stage 2, up to 36 additional subjects will be enrolled for a total of 51. If fewer than 22 (43%) responders (PR or CR) are observed in 51 subjects, consideration may be given to conclude that the treatment schedule does not warrant further study in this population. The final evaluation of each schedule will be based on the totality of data observed, including types of responses, safety data, and discontinuation rates. This design yields a type I error rate of 0.025 (1-sided) and power of 90% under the assumptions described above.

Subjects will be stratified by number of prior therapies (1 or  $> 1$ ), bulky disease status (longest diameter of baseline lesion  $< 5$  cm or  $\geq 5$  cm) and time since last recurrence ( $\geq 24$  months or  $< 24$  months).

Note: "Enrolled" means subjects', or their legally acceptable representative's, agreement to participate in a clinical study following completion of the informed consent process. Potential subjects who are pre-screened for the purpose of determining eligibility for the study but do not sign an informed consent form (ICF) are not considered enrolled.

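### The Stage 1 exit for concluding ORR exceeds 30% has no responder threshold and no alpha allowance, so the stated one-sided 0.025 does not cover it

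*Protocol*

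**What the plan says.** Protocol 9.1 sets the null for each arm at ORR 30% or less and the alternative at 55% or more. Protocol 9.2 and SAP 4.13 describe two stages per arm: 15 subjects, then up to 36 more, for a total of 51. The lower Stage 1 boundary is advisory: "If there are fewer than 6 responders (PR or CR) among the first 15 subjects, consideration may be given to terminating the treatment arm". Fewer than 22 responders among 51 may lead to a conclusion that the schedule does not merit further study.

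The same sections let an arm omit Stage 2 for a favourable reason. In the SAP's words, "A treatment arm may also not proceed to the second stage if the totality of the data is compelling" (section 3.1). Protocol 9.2 gives the example: "such scenarios could include (but are not limited to) accumulating enough data in Stage 1 to conclude the ORR exceeds 30" percent. No responder count, test level or share of alpha goes with it.

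SAP 4.13 then states: "This design yields a type I error rate of 0.025 (1-sided) and power of 90% under the assumptions described above". Protocol 9.2 also says alpha is controlled at 0.025. SAP 4.10.1.5 says "No formal interim analysis is planned", and Protocol 9.5 agrees, while both describe an evaluation of each arm at the end of Stage 1. The only inferential method given for ORR is the "2-sided 95% exact CI using the Clopper-Pearson exact method for binomial proportions" (SAP 4.10.2).

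**The concern.** Concluding that ORR exceeds 30% is the same as rejecting the primary null. If an arm may do so on Stage 1 data, and otherwise goes on to a final test of the same null at 51 subjects, it has two chances to reject. The stated error rate allows for one. Obeying the 6/15 futility stop does not cure this, because the extra error comes from the upper end of the Stage 1 distribution.

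The exit would often be reached if the drug works. At the assumed 55% ORR, 45% of arms would show 9 or more responders among 15. What is at stake is whether the type I error attached to an early claim is true. The study is open-label, response is investigator-assessed and there is no data monitoring committee, so a numerical boundary is the main safeguard available.

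**Working it through.** **Inputs.** p0 = 0.30 and p1 = 0.55 (Protocol 9.1); n1 = 15, futility below 6, total 51, final cut-off 22 (Protocol 9.2, SAP 4.13). The Stage 1 success threshold s is not in either document, so it is varied from 8 to 11.

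**The plan's own figure.** With no success exit,

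P(reject) = Σ over x = 6..15 of Bin(x; 15, p) × P(Bin(36, p) ≥ 22 − x).

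At p = 0.30 this is 0.0246 and at p = 0.55 it is 0.9035. The stated 0.025 and 90% are therefore reproduced, for a futility-only design with 6/15 enforced. If 6/15 is never enforced, alpha is 0.0319.

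**Where the exact interval first excludes 30%.** Lower 95% Clopper-Pearson limits are 26.6% for 8/15 and 32.3% for 9/15; 29.3% for 22/51 and 31.1% for 23/51.

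**Adding the exit.**

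alpha = P(Bin(15, 0.30) ≥ s) + Σ over x = 6..s−1 of Bin(x; 15, 0.30) × P(Bin(36, 0.30) ≥ 22 − x).

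For s = 9 the first term is 0.0152. The second is 0.14724 × 0.04704 + 0.08113 × 0.09166 + 0.03477 × 0.16266 = 0.00693 + 0.00744 + 0.00566 = 0.0200. The total is 0.0353 before rounding of the parts. With futility optional, the sum runs from x = 0.

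| Stage 1 success at | Alpha, 6/15 binding, final 22/51 | Alpha, 6/15 optional, final 22/51 | P(early success) at ORR 55% |
|---|---|---|---|
| 11/15 | 0.0249 | 0.0322 | 12% |
| 10/15 | 0.0267 | 0.0340 | 26% |
| 9/15 | 0.0353 | 0.0425 | 45% |
| 8/15 | 0.0644 | 0.0717 | 65% |

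**What a 9/15 claim means under the null.** Arms that reach 9/15 and would also reach 22/51 contribute 0.0246 − 0.0200 = 0.0046 to alpha. That is 0.0046 / 0.0152 = 30% of arms reaching 9/15, so about 70% of such arms at a true 30% would have missed 22/51 had they continued.

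**Exact interval at both looks.** With 9/15 and then 23/51, alpha is 0.0255 if 6/15 is binding (0.0132 without the exit) and 0.0284 if optional. Power with 6/15 binding is 88.9%.

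**Overrun.** Enrollment is continuous between stages, so the look may include more than 15 subjects. Futility is kept on the first 15, success is judged by the exact interval on all subjects in the look, and the final cut-off is 22/51:

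| Subjects in look | Success at | Alpha, binding | Alpha, optional |
|---|---|---|---|
| 18 | 10 | 0.0389 | 0.0462 |
| 19 | 11 | 0.0309 | 0.0381 |
| 20 | 11 | 0.0354 | 0.0427 |

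The values are not monotone because the counts are discrete.

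**The case against.** The clause governs whether to enrol further, not a test. It sits under a totality-of-data decision in a proof-of-concept study (Protocol 2.1), no Stage 1 test is written, and the primary ORR analysis is set for 12 months after the last randomization (SAP 4.10.2). Compelling could mean a bar well above bare exclusion of 30%. Both documents also disclose the Stage 1 evaluation openly.

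Part of this stands: the second chance to reject is inferred from the wording and is not a written decision rule. But the example names the conclusion that defines rejection of the null, and a plan that claims controlled alpha cannot leave a route to that conclusion undefined.

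A reader might go further and infer that the true alpha is about 0.035. The documents do not support that as an unconditional figure. It takes 9/15 as the threshold, which is an assumption, and it uses the exact interval at Stage 1 but the 22/51 cut-off at the end. Under the exact interval at both looks, with 6/15 binding, the total is 0.0255, close to nominal. At 11/15 with 22/51 there is no excess at all.

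**Conclusion.** The point holds in a conditional form. The stated 0.025 and 90% describe a futility-only design. The written rules add a success exit without a threshold, so their type I error is undetermined. With 22/51 as the final rule it runs from 0.0249 (11/15) to 0.0644 (8/15) if 6/15 is obeyed, and from 0.0322 to 0.0717 if it is not. Of the thresholds examined, only 11/15 with a binding 6/15 stays within 0.025 when the final cut-off is 22.

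All figures are per arm at a true ORR of exactly 30%. They assume that an early stop for this reason is reported as a conclusion that ORR exceeds 30%. The plan should be corrected, but the size of the excess cannot be stated as a single number.

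**What to change.** In Protocol 9.2 and SAP 3.1 and 4.13 (and the matching note to Protocol Figure 2), adopt one of the following.

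- **(a) No Stage 1 claim.** Delete the example about concluding that ORR exceeds 30%, and state that an arm closed at Stage 1 makes no formal claim of ORR above 30%. With 6/15 made binding, alpha is 0.0246 and power 90.4%. This is the simplest change.
- **(b) A fixed boundary.** Allow a Stage 1 claim only with at least 11 responders among the first 15 treated subjects in the arm, and in the same edit make the 6/15 stop binding for the alpha claim. Alpha is 0.0249 and power 90.4%. Changing the success clause alone would leave alpha at 0.0322.
- **(c) If 6/15 must stay optional.** Use at least 10/15 at Stage 1 and at least 23/51 at the end. Alpha is 0.0187 and power 94.2% if futility is never enforced; power is 88.6% if it is, so the power statement must be revised.

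In each case, describe the Stage 1 look as an interim analysis in Protocol 9.5 and SAP 4.10.1.5.

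The documents do not say whether Stage 1 results have been reviewed; SAP 3.0 is dated August 2023 and follows dry-run comments. If they have been seen, use (a), or report alpha as conditional on the threshold, because a boundary set afterwards would be post hoc.

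The cost is wording, with no subjects beyond the planned 51 per arm. Early success stops become rarer: at 55% ORR, from 45% of arms at 9/15 to 26% at 10/15, 12% at 11/15, or none under (a). Under (a), the 90.4% power assumes that no promising arm is closed early for another reason.
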